### **10.4.2 Analysis of Secondary Endpoint(s)**

Clinical performance and safety of the [REDACTED] NPWT system over a 30 day follow-up period will be presented separately for each specialty, and will include:

- Incidence of Surgical Site Infection (SSI) – Superficial, deep, organ [CDC criteria] within 30 days of surgery

#### **CONFIDENTIAL AND PROPRIETARY**

This document contains information that is confidential and proprietary to Smith & Nephew PLC and Smith & Nephew, Inc. and is intended for use only by Smith & Nephew and its manufacturer. It shall not be reproduced or copied in whole or in part, nor shall the contents be disclosed by any means without prior written permission from Smith & Nephew, nor shall anyone make any use of it that is contrary to the expressed or implied wishes of Smith & Nephew.

[REDACTED] - [REDACTED] - [REDACTED]

Smith+Nephew

**Clinical Protocol - Device****Pre-Registration Clinical  
Study**

Study Number:  
CT1705POB  
Version: 9.0 04Aug2021  
Page: 86 of 221

- Incidence of Surgical site Complications (SSC) [as applicable: dehiscence (superficial/deep, partial/total), seroma, necrosis, hematoma, suture abscess] within 30 days of surgery
- Wound and Skin VAS score assessment at 7, 14 and 30 days
- Condition of peri-wound skin and skin under the pump [REDACTED] assessed through visual inspection at 7, 14 and 30 days.
- Level of pain during wear of the [REDACTED] system, and at dressing removal assessed by VAS scale following 7-day therapy
- Phase 1 only: Comparison of Wound and Skin VAS scores at days 7, 14 and 30 as assessed by the treating clinicians versus scores provided by the independent assessor.
- Phase 1 only: Range of motion assessment (ROM) for the knee at pre-operative visit, post-operative visit, 7, 14 and 30 days.
- Level of pain during dressing removal (VAS scale) - pain intensity as none, mild, moderate, or severe.

For incidence of SSI and incidence of SSC binary variables indicating presence of/absence of will be defined and the frequencies together with percentages reported/identified outcomes will be reported separately for each specialty. A logistic model will be used to evaluate the adjusted and the un-adjusted models for the secondary variables, the incidence of surgical site infections, and incidence of surgical complications separately for each specialty. The variables considered important and to be included in the final model are Age, Diabetic status and the presence of any other co-morbidity as a binary variable. All other baseline and medical factors collected at baseline will be evaluated for importance in adjusted models and only those statistically significant in an un-adjusted model will be considered in the final model.

Where the data is recorded both by the treating investigator, and by an independent medically qualified individual/assessor (for example, the wound and skin VAS score), the assessments will be presented separately for each assessor and results cross-tabulated

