## **7.7 Lost to Follow-up**

A subject will be considered lost to follow-up if he/she does not appear for the 7 day, 14 day, or 30 day visit and study personnel are unable to contact the subject.

Some actively enrolled subjects will not return for follow-up exams on time. Study personnel must make a reasonable effort to contact the subject and document the following contact attempts prior to declaring a subject to be lost to follow-up: the subject has been contacted according to the site's policies, but no fewer than 2 documented phone contacts and 1 certified letter without response. Copies of all attempts to reach the subjects per regular mail or email and/or the attempts to contact the subject via other means should be documented and that documentation should be kept with the subject's source documents.

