## **Clinical Protocol - Device**

### **Pre-Registration Clinical Study**

Study Number:  
CT1705POB  
Version:9.0 04Aug2021  
Page: 70 of 221

1. Record the date that the complication occurred.
2. Record the complication type. Please provide as much detail as possible.
3. Record procedure (e.g. opening of wound, drainage of wound infection, antibiotics—oral, antibiotics—intravenous, re-suture of wound, evacuation of hematoma, seroma aspiration, incision of an abscess, wound toilet, negative pressure wound dressing—cavity, change to antimicrobial or antibacterial treatment, other)/treatment changed to (e.g. a different NPWT system, simple foam dressing, antimicrobial dressing, other). Photograph the incision using the camera (██████████) supplied by the Sponsor. The wound photographs and the resulting wound measures will be stored in a database. Record 100mm VAS score for wound and skin assessment.
4. Record any concomitant medications.
5. The complication and any device deficiencies must be recorded as instructed in Section 12 - Adverse events and device deficiencies.

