### **9.1.11 Discontinued Subjects**

Discontinued subjects are those who voluntarily discontinue participation or who are lost to follow-up refer to section 7.8 for further details. Where possible, a full Exit Visit should be completed for all subjects who discontinue the study early. Where consent is withdrawn, the date and any reason given for discontinuation should be captured, at a minimum (see Section 7.8.2).

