## CONFIDENTIAL AND PROPRIETARY

This document contains information that is confidential and proprietary to Smith & Nephew PLC and Smith & Nephew, Inc. and is intended for use only by Smith & Nephew and its manufacturer. It shall not be reproduced or copied in whole or in part, nor shall the contents be disclosed by any means without prior written permission from Smith & Nephew, nor shall anyone make any use of it that is contrary to the expressed or implied wishes of Smith & Nephew.

[REDACTED] - [REDACTED] - [REDACTED]

**Smith+Nephew****Clinical Protocol - Device****Pre-Registration Clinical  
Study**

Study Number:  
CT1705POB  
Version:9.0 04Aug2021  
Page: 75 of 221

An internal analysis of previously reported level one studies showed the incidence of SSCs in abdominal surgery treated with PICO was 8.2%, (compared to 23.4% in controls).  There is only one study reporting knees alone, with most studies combining both knee and hip arthroplasty, making analysis difficult, and S+N had previously agreed that such studies would not be included. In the study which reported knees alone SSCs were reported in 34% of cases in the PICO group, compared to 77% in the control group.

Results from this trial will be also compared to actually reported rates of SSC in each one of the research centres (where available) for the concerned specialty and types of surgery.

This assessment will be intended to ensure that [REDACTED] is not compromising subjects' safety and importantly will be a clinical comparison, rather than a statistical comparison.

[REDACTED]

[REDACTED]

A training session will be held for the individuals at each site to standardise how the pictures must be taken and the assessments of complication, infection and dehiscence made.

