### **9.2.4 Photographs and Surgical Site Assessment**

Images of the subject's postsurgical incision (and wound zone) will be captured prior to initial dressing application, at 7 days post operatively (or when dressing is removed), at 14 days and at 30 days postoperatively (or early exit visit) using a digital camera supplied by S&N.

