## 10.2 Analysis Populations

- Safety Population (SAF), including all subjects who have received the study device.
- Full analysis set population (FAS), following ITT principle including all subjects recruited into the study.
- Per-Protocol Population 1 (PP), including all subjects in the full analysis set who have no significant protocol deviations and met the inclusion/exclusion criteria.

Statistical analysis will be performed using each of the subject populations as follows. Analysis of the primary, secondary and exploratory performance objectives will be performed separately using both the Full Analysis Set and the Per Protocol Population. All safety analyses will utilize the Safety Population, separately for each specialty.

Subsets of the above populations will be used for secondary analyses where appropriate to analyse only those subjects in the abdominal group who were recruited post-interim analysis and followed version 8.0 of the protocol. These subset populations will be labelled with the prefix "s-" so it is clear, for example the subset of the full analysis set will be labelled s-FAS etc.

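### 30-day SSI and SSC are reported as simple present/absent percentages, with no rule for subjects whose follow-up ends before day 30

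*Combined protocol and SAP*

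**What the plan says.** All references are to the combined protocol and SAP, version 9.0.

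- **Endpoint.** Section 10.4.2 lists "Incidence of Surgical Site Infection (SSI) – Superficial, deep, organ [CDC criteria] within 30 days of surgery", and SSC over the same window.
- **Analysis.** The same section says "For incidence of SSI and incidence of SSC binary variables indicating presence of/absence of will be defined and the frequencies together with percentages" of the reported or identified outcomes will be given, with logistic models. It mentions no person-time, censoring, missing category or sensitivity analysis, and names no confidence interval for SSI/SSC. Section 10.1 promises intervals only in general, where appropriate.
- **Denominator.** Section 10.2: "Full analysis set population (FAS), following ITT principle including all subjects recruited into the study". A per-protocol analysis is also planned.
- **Early leavers.** Section 9.1.11: "Where possible, a full Exit Visit should be completed for all subjects who discontinue the study early". The visit schedule includes the incision complications assessment in its unscheduled/early-exit column, and 9.2.4 lets the early exit visit stand in for day 30 for incision images.
- **Loss to follow-up.** Under 7.7 a subject is lost "if he/she does not appear for the 7 day, 14 day, or 30 day visit and study personnel are unable to contact the subject", after at least two documented telephone contacts and one certified letter have gone unanswered.
- **Dates.** Section 9.1.9, step 1: "Record the date that the complication occurred".
- **Use of the rate.** Section 9.2.1 compares the secondary endpoint results with published data and gives 8.2% as the SSC incidence in abdominal surgery with PICO (23.4% in controls). It then plans a comparison with each centre's own reported rates and adds: "This assessment will be intended to ensure that [REDACTED] is not compromising subjects' safety". It describes this as a clinical and not a statistical comparison.

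**The concern.** A 30-day incidence needs either 30 days of observation in everyone or a method that allows for shorter observation. The plan supplies neither. A subject who leaves on day 8 can have a completed complication assessment showing none. A subject who misses day 14 and cannot be reached can be declared lost with the day-30 window still ahead. After exit, section 12.5 follows adverse events that are still ongoing, so a new complication on day 20 has no stated route into the data.

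With a present/absent variable, a numerator of reported outcomes and a denominator of everyone recruited, the natural default is that such a subject counts as 'absent'. That coding can only lower the percentage, and the percentage feeds a judgement about safety. The regulator's no-objection letter (Appendix 22.13) also asks for each endpoint to be set against a comparable published result, which requires the trial's own 30-day figure to be well defined.

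**Working it through.** **Inputs from the documents.** True SSC rate p = 8.2% (9.2.1, taken as the truth for illustration); share leaving early d = 15% (11.1); abdominal N = 66 in total, 44 of them in phase 2 (11.2).

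**Inputs assumed.** F, the share of leavers' 30-day complications already seen when they leave, is not in the documents; range 0 to 0.75. The documents also do not say how many leavers would attend an early Exit Visit. The planning loss is used as d for all early leavers.

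**The plan's attrition figure.** 38 × 1.15 = 43.7, rounded up to 44, as stated. Dividing instead, 38 / 0.85 = 44.7, or 45. The 15% is therefore the plan's working figure.

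**Reported rate if event-free leavers are coded 'absent' and leaving is unrelated to risk.** Reported = p × [(1 − d) + d × F].

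| F | Calculation | Reported | Bias (points) | Events missed in 66 |
|---|---|---|---|---|
| 0 | 8.2% × 0.85 | 6.97% | −1.23 | 0.81 |
| 0.25 | 8.2% × 0.8875 | 7.28% | −0.92 | 0.61 |
| 0.5 | 8.2% × 0.925 | 7.58% | −0.62 | 0.41 |
| 0.75 | 8.2% × 0.9625 | 7.89% | −0.31 | 0.20 |

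In 44 subjects the shortfall is 0.14 to 0.54 of an event. With 5% leaving, the bias is −0.1 to −0.4 points.

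**Scale against sampling error.** The nearest whole count to 8.2% of 66 is 5: 5/66 = 7.6%, exact 95% CI 2.5% to 16.8%. For 4/44 = 9.1%, it is 2.5% to 21.7%.

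**If leaving is related to risk.** Assume leavers carry twice the risk, all leave on day 7, and events are spread evenly over 30 days.

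- True rate: 8.2% × (0.85 + 0.30) = 9.4%.
- Reported, coded 'absent': 8.2% × (0.85 + 0.30 × 7/30) = 7.5%.
- Kaplan-Meier: risk to day 7 is 0.85 × 8.2% × 7/30 + 0.15 × 16.4% × 7/30 = 2.2%. Among those who stay, the risk from day 7 to day 30 is (8.2% − 1.9%) / (100% − 1.9%) = 6.4%. The estimate is 1 − 0.978 × 0.936 = 8.5%.

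Kaplan-Meier therefore closes about half of this gap. When leaving is unrelated to risk it recovers the truth: 1 − 0.981 × 0.936 = 8.2%.

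**Best/worst-case range.** 15% of 66 is about 10 subjects. With 5 observed events, the rate is 5/66 = 7.6% if none of the 10 had a later SSC and 15/66 = 22.7% if all did.

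**A tempting alternative that fails.** A crude rate among subjects with an event or an assessment at day 27 or later keeps leavers' events but drops event-free leavers. With exits at day 7 and unrelated risk, events are 8.2% × (0.85 + 0.15 × 7/30) = 7.26% of all subjects and event-free completers are 0.85 × 91.8% = 78.0%. The rate is 7.26 / (7.26 + 78.0) = 8.5% when the truth is 8.2%, so it is biased upward.

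**The case against.** A reader might infer that the plan counts a subject followed for 8 days as complication-free, and that the rate set against 8.2% is therefore known to be too low. The documents do not support that, for these reasons.

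- **Coding.** Section 10.4.2 says the variables will be defined. It does not say that partial follow-up is scored 'absent'. Setting such subjects to missing remains open, and section 10 leaves detail to a separate SAP, of which the reviewed documents contain no text.
- **Who is affected.** Subjects lost under 7.7 cannot be reached, so most would have no early Exit Visit and their last assessment would be missing. Stopping treatment alone does not end study participation (9.1.11).
- **Partial safeguard.** Uncollected data points are deviations (8.3.1) and significant deviations remove a subject from the per-protocol set (10.2), so some partly followed subjects may drop out of that analysis.
- **Benchmark.** The 8.2% is for SSC, not SSI. The comparison has no margin or threshold, so falling on one side of 8.2% changes no decision rule. How the source studies handled incomplete follow-up is not given, so the net bias of the comparison is unknown.
- **Size.** Without informative leaving, the effect is under one event in 66, well inside sampling error.

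All of this stands and limits the claim. It does not remove the gap. Setting leavers to missing conflicts with an all-recruited analysis set and has its own bias if leaving relates to complications. What counts as a significant deviation is undefined. The SAP need only be final before database lock in an unblinded single-arm study (8.1), so the rule could be chosen with outcomes visible.

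**Conclusion.** The concern holds in a limited form. The plan reports 30-day SSI and SSC as crude percentages with no allowance for follow-up that ends early, and its natural reading keeps event-free leavers in the denominator as 'absent'. If so coded, the bias is downward: about 0.3 to 1.2 points on a true 8.2% at 15% loss. This rests on 8.2% being the true rate, on 15% leaving the study, and on leaving being unrelated to complications. Under an assumed doubled risk in leavers it would be larger, with 9.4% reported as 7.5%, but nothing in the documents gives the risk in leavers. This is a worthwhile, cheap improvement to a safety estimate and not evidence that the trial's safety conclusion would be wrong.

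**What to change.** - **Section 10.4.2 and the SAP.** Estimate 30-day SSI and SSC incidence by Kaplan-Meier at day 30 with a 95% CI. Use the recorded complication dates and censor event-free subjects at their last assessment.
- **Beside it.** Report the number of event-free subjects without an assessment in the day 30 (±3) window, and a best/worst-case range. The range is needed because Kaplan-Meier assumes that censoring is unrelated to risk and only partly corrects informative leaving. Do not use the crude rate among subjects with an event or a late assessment as the companion figure.
- **Section 7.7.** Do not finalise lost-to-follow-up status for SSI/SSC until the day 30 (+3) window has closed, so that a missed day 7 or day 14 visit does not by itself end outcome follow-up.

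**Cost.** A few sentences in 10.4.2 and the SAP and one in 7.7. The dates are already collected, and no extra visit or procedure is needed. The reported rate will be slightly higher and slightly less precise.

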## CONFIDENTIAL AND PROPRIETARY

This document contains information that is confidential and proprietary to Smith & Nephew PLC and Smith & Nephew, Inc. and is intended for use only by Smith & Nephew and its manufacturer. It shall not be reproduced or copied in whole or in part, nor shall the contents be disclosed by any means without prior written permission from Smith & Nephew, nor shall anyone make any use of it that is contrary to the expressed or implied wishes of Smith & Nephew.

[REDACTED] - [REDACTED] - [REDACTED]

**Clinical Protocol - Device****Pre-Registration Clinical  
Study**

Study Number:  
CT1705POB  
Version:9.0 04Aug2021  
Page: 87 of 221

between assessors where appropriate. In each case analyses will be presented separately for each specialty.

Summary statistics for all other secondary variables will be given, for each specialty separately, according to the nature of the variable, continuous or categorical. For categorical variables, the number of observations, mean, standard deviation, median, minimum, and maximum will be presented, while for categorical variables the number of observations, frequency, and percentages will be reported. 95% confidence intervals will be reported where appropriate.

As range of motion is collected for subjects in the knee surgery group only there will be no summary of ROM in the s-FAS and s-PP analysis.

### **10.4.3 Analysis of Exploratory Endpoints**

- Acceptability (clinician/subject questionnaires)
- Subject comfort during wear (subject questionnaire)
- Ease of application & removal

All exploratory end points will be summarised through descriptive statistics and tabulated accordingly, separately for each specialty. For categorical variables, the number of observations, mean, standard deviation, median, minimum, and maximum will be presented, while for categorical variables the number of observations, frequency, and percentages will be reported. 95% confidence intervals will be reported where appropriate.

### **10.5 Safety Analyses**

- Adverse Events and Device Deficiencies

## **Clinical Protocol - Device**

### **Pre-Registration Clinical Study**

---

Study Number:  
CT1705POB  
Version:9.0 04Aug2021  
Page: 88 of 221

All safety analyses and summaries will be conducted using the Safety Population. All safety summaries will be presented by specialty in conjunction with selected demographic variables e.g. gender.

## **10.6 Interim Analyses**

As a condition for the MHRA No Objection decision, an interim analysis was required to be performed once the study has recruited 22 subjects in each specialty group who had completed the follow-up period. The study was paused while the MHRA assessed the results.

There will be no further interim analysis performed as part of Phase 2 of this study.

## **11 SAMPLE SIZE JUSTIFICATION**

### **11.1 Sample Size Justification Pre-Interim Analysis**

The sample size is justified based on the proposed three primary outcome variables of nominal pressure of 80mmHg, Dressing wear time in days and exudate management based

**CONFIDENTIAL AND PROPRIETARY**

This document contains information that is confidential and proprietary to Smith & Nephew PLC and Smith & Nephew, Inc. and is intended for use only by Smith & Nephew and its manufacturer. It shall not be reproduced or copied in whole or in part, nor shall the contents be disclosed by any means without prior written permission from Smith & Nephew, nor shall anyone make any use of it that is contrary to the expressed or implied wishes of Smith & Nephew.

---

**Clinical Protocol - Device****Pre-Registration Clinical  
Study**

Study Number:  
CT1705POB  
Version:9.0 04Aug2021  
Page: 89 of 221

on incidence of exudate leakage. Each of the three hypotheses will be tested separately for each specialty cohort.

For the nominal pressure the sample size is based on analysis to test equivalence of negative pressure delivery against the reference value of 80.2mmHg. Previous data extracted from the PICO 7 system were found to be distributed with a SD=14.8. For purposes of sample size calculation, the a priori assumption is that the [REDACTED] system will have a similar operating pressure to PICO 7, and therefore similar variability in pressure delivery is assumed. The following hypotheses will be tested to establish the equivalence in mean operating pressure of [REDACTED] system over 7 days compared to the reference value for PICO 7 (80.2 mmHg) with equivalence margin,  $\delta_1$ :

$$H_0: |\mu - \mu_0| \geq \delta_1$$

$$H_a: |\mu - \mu_0| < \delta_1$$

In the stated hypotheses,  $\mu$  represents the mean operating pressure of [REDACTED] system and  $\mu_0$  represents , the reference value relating to the mean operating pressure of PICO 7 (=80.2mmHg, SD=14.8). The equivalence margin,  $\delta_1 = 7$  mmHg was chosen as a conservative non-clinically significant difference for operating pressure assuming the difference is actually 0. The hypothesis will be tested, separately for each specialty cohort by a two-sided t-test (TOST) at the alpha level of 0.025 (one-sided). If the null hypothesis is rejected, clinical equivalence in terms of pressure delivery will be confirmed.

Based on the data used for sample size estimation, thirty eight (38) subjects are required to achieve 80% power to detect equivalence at the significance level of  $\alpha = 0.025$  (one-sided) within 7mmHg using a two-sided t-test. Drawing from past experience, allowing that 15% of the subjects may be lost to follow up by the end of the study, a sample size of 44 subjects

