### **10.4.1 Analysis of Primary Endpoint(s)**

- Negative Pressure maintenance at nominal 80mmHg

The following hypotheses will be tested to establish equivalence of the [REDACTED] compared to the internally derived value, with equivalence margin,  $\delta_1 > 0$ , for each specialty cohort:

$$H_0: |\mu - \mu_0| \geq \delta_1$$

$$H_a: |\mu - \mu_0| < \delta_1$$

In the stated hypotheses,  $\mu$  represents the assumed mean operating pressure (80.2 mmHg) and  $\mu_0$  represents the mean [REDACTED] operating pressure. The equivalence limit  $\delta_1 = 7\text{mmHg}$  was chosen as a conservative non-clinically significant difference assuming that the difference is actually 0. The hypothesis will be tested by two-one-sided t-test (TOST)

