## CONFIDENTIAL AND PROPRIETARY

This document contains information that is confidential and proprietary to Smith & Nephew PLC and Smith & Nephew, Inc. and is intended for use only by Smith & Nephew and its manufacturer. It shall not be reproduced or copied in whole or in part, nor shall the contents be disclosed by any means without prior written permission from Smith & Nephew, nor shall anyone make any use of it that is contrary to the expressed or implied wishes of Smith & Nephew.

[REDACTED] - [REDACTED] - [REDACTED]

Smith+Nephew

**Clinical Protocol - Device****Pre-Registration Clinical  
Study**

Study Number:  
CT1705POB  
Version: 9.0 04Aug2021  
Page: 84 of 221

at the alpha level of 0.025 (one-sided), separately for each specialty. If the null hypothesis is rejected, equivalence will be confirmed.

The corresponding 95% CI for each cohort will also be presented.

- Dressing wear time in days as assessed through a combination of data from [REDACTED] and CRF recorded data of any unplanned dressing change.

The following hypotheses will be tested, for each specialty separately, to establish that the dressing wear time of the [REDACTED] pump system is strictly no worse (lower) than the literature derived value:

$$H_0: \mu - \mu_0 \leq 0$$

$$H_a: \mu - \mu_0 > 0$$

In the stated hypothesis,  $\mu$  represents the mean [REDACTED] dressing wear time in days and  $\mu_0$  represents the literature derived value (4.6 days). A one sided (one sample) t-test with alpha = 0.025 will be used to evaluate the hypothesis for each specialty, the corresponding 95% CIs will also be presented. A binary variable indicating  $<7$  /  $\geq 7$  days wear time (denoted by 0/1) will also be used and the proportion of dressings with a wear time  $\geq 7$  days will be reported as a percentage along with corresponding 95% confidence interval, for each specialty cohort. If necessary and if data allows, important associated factors will be adjusted for in a logistic model.

- Exudate management assessed by no occurrence of exudate leaks as assessed by reported clinical data on any exudate leakage observed through a dressing or around the borders during the dressing wearing period resulting or not, in an unplanned dressing change.

A binary variable for the non-leakage and leakage will be used and the proportion of reported/identified leaks will be presented as a frequency together with a percentage and a

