## CONFIDENTIAL AND PROPRIETARY

This document contains information that is confidential and proprietary to Smith & Nephew PLC and Smith & Nephew, Inc. and is intended for use only by Smith & Nephew and its manufacturer. It shall not be reproduced or copied in whole or in part, nor shall the contents be disclosed by any means without prior written permission from Smith & Nephew, nor shall anyone make any use of it that is contrary to the expressed or implied wishes of Smith & Nephew.

[REDACTED] - [REDACTED] - [REDACTED]

**Smith+Nephew****Clinical Protocol - Device****Pre-Registration Clinical  
Study**

Study Number:  
CT1705POB  
Version: 9.0 04Aug2021  
Page: 90 of 221

per specialty are needed to achieve sufficient statistical power for each specialty to be analysed separately, within this study.

Based on the above, a total of 88 subjects will be recruited, which will include 44 subjects with each of the following specialties: orthopaedics (closed surgical knee incisions, e.g. after total knee arthroplasty), and abdominal surgery (e.g. closed surgical abdominal incisions of which at least 50% would be colorectal cases).

For the management of exudate, measured by incidence of exudate leakage, the sample size is evaluated for adequacy based on the non-leakage rate recorded by the NWPT system. According to internal data collected within Smith and Nephew surgical study involving Closed Abdominal and Orthopaedic subjects, 85% of the PICO NPWT systems had no exudate leaks. Therefore, assuming that [REDACTED] NWPT system will manage 85% of exudate effectively or better, demonstrated through no exudate leakage observed, a sample size of 10 subjects for each specialty will be sufficient to exclude a response rate of 65% or less with 80% power by using a 2-sided 95% confidence interval for orthopaedics (closed knee incisions e.g. after Total Knee Arthroplasty), and Abdominal surgery (closed abdominal surgical incisions) separately. With the planned 44 subjects per specialty, a response rate below 70% could be excluded for each specialty individually.

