**CONFIDENTIAL AND PROPRIETARY**

This document contains information that is confidential and proprietary to Smith & Nephew PLC and Smith & Nephew, Inc. and is intended for use only by Smith & Nephew and its manufacturer. It shall not be reproduced or copied in whole or in part, nor shall the contents be disclosed by any means without prior written permission from Smith & Nephew, nor shall anyone make any use of it that is contrary to the expressed or implied wishes of Smith & Nephew.

[REDACTED] - [REDACTED] - [REDACTED]

**Clinical Protocol - Device****Pre-Registration Clinical  
Study**

Study Number:  
CT1705POB  
Version:9.0 04Aug2021  
Page: 92 of 221

The 2nd phase of the study (post-interim analysis) will be powered according to previous sample size. However, as no further subjects will be recruited for the orthopaedic surgery group, all 44 subjects recruited will be in the abdominal indication group. This will increase the total number of abdominal incisions to 66 (22 recruited following the protocol v7.0 and 44 following v8.0 of the protocol). This ensures that the primary endpoint is sufficiently powered for both the primary analysis of the abdominal data for all subjects as well as for a secondary analysis to be done on the data from those recruited according to protocol v8.0 only.

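### The 38 subjects said to give 80% power for pressure equivalence give 62% under the planned TOST, so the phase 2-only analysis is not adequately powered on the plan's own inputs

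*Combined protocol and SAP*

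**What the plan says.** Section 11.1 bases the sample size on three primary outcome variables, each with its own hypothesis. For negative pressure it compares the mean with a fixed reference of 80.2 mmHg, using a margin of 7 mmHg and an assumed true difference of 0. The spread comes from PICO 7 data, "found to be distributed with a SD=14.8".

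The test is described as a "two-sided t-test (TOST) at the alpha level of 0.025 (one-sided"). Section 10.4.1 also specifies a TOST, "at the alpha level of 0.025 (one-sided), separately for each specialty", and reports a 95% confidence interval alongside it.

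Section 11.1 then says that "thirty eight (38) subjects are required to achieve 80% power to detect equivalence", "within 7mmHg using a two-sided t-test". It raises 38 to 44 for 15% loss and says that 44 subjects "per specialty are needed to achieve sufficient statistical power for each specialty to be analysed separately".

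After the interim analysis, Section 7.1 and Section 11.2 keep the earlier sample size as the basis for phase 2, with all 44 new subjects abdominal. Section 11.2 and the synopsis conclude: "This ensures that the primary endpoint is sufficiently powered for both the primary analysis of the abdominal data for all subjects". The same sentence goes on to make that claim for the secondary analysis of subjects recruited under v8.0. Sections 10.2 and 10.4 define that analysis as s-FAS and s-PP.

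**The concern.** In a TOST, equivalence is shown only if both one-sided tests reject, that is, if the 95% interval lies wholly inside ±7 mmHg. When the true difference is 0, either side can fail, so the type II error is shared between two tests. The sample size must then be larger than for a single test of a 7 mmHg shift. The 38 is stated next to a two-sided t-test, which suggests that the single-test formula was used.

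The figure is not only historical. Phase 2 is still justified by it, and the current text says the v8.0-only analysis is adequately powered. The study supports a CE-marking submission. A reader who trusts that statement could take a failed equivalence test in the phase 2 set as a finding about the device, when the set was simply too small.

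**Working it through.** **Inputs** (Section 11.1; test and alpha also in 10.4.1): one-sample design, reference 80.2 mmHg, margin δ = 7, σ = 14.8, true difference d = 0, one-sided α = 0.025 per test, target power 80%, loss 15%. From Section 11.2: 66 abdominal subjects in all, of whom 44 are under v8.0.

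**Step 1: reproduce 38.** For a single one-sample t-test of a 7 mmHg shift, power = P(T > t(0.975, n−1)), where T is noncentral t with noncentrality δ√n/σ.

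- n = 37: 79.9%
- n = 38: 81.0%

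So 38 is exactly the smallest n reaching 80% for a single test.

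**Step 2: the planned TOST.** Let h(s) = δ − t(0.975, n−1)·s/√n. Given the sample SD s, equivalence is concluded when the observed difference lies within ±h(s). Power is the average over the distribution of s, for values of s with h(s) > 0, of

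Φ((h(s) − d)/(σ/√n)) − Φ((−h(s) − d)/(σ/√n)).

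A hand check with σ known, for n = 38: δ√n/σ = 7 × 6.164/14.8 = 2.916. Subtracting 1.960 leaves 0.956, and Φ(0.956) = 0.830. Power is then 2 × 0.830 − 1 = 66%. Using the t distribution lowers this to 62%.

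Exact results at d = 0:

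| Evaluable n | What it represents | TOST power |
|---|---|---|
| 38 | stated as 80% | 62.1% |
| 48 | | 78.8% |
| 49 | first n reaching 80% | 80.1% |
| 44 | phase 2 only, no loss | 73.2% |
| 37 | phase 2 only, 15% loss (44 × 0.85 = 37.4) | 59.9% |
| 66 | all abdominal, no loss | 93.2% |
| 56 | all abdominal, 15% loss (66 × 0.85 = 56.1) | 87.1% |

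Simulation with 400,000 replicates gives 62.1% at n = 38, 73.2% at n = 44 and 80.1% at n = 49.

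**Step 3: could another TOST reading give 38?** At 0.05 per side, 38 subjects give 77.6% and 80% needs 40. That alpha does not give 38 exactly, and it contradicts the stated 0.025 and the paired 95% interval. The normal approximation to TOST at 0.025 gives ((1.960 + 1.282) × 14.8/7)² = 46.97, so 47.

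**Step 4: sensitivity.**

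- SD: the phase 2-only analysis reaches 80% only if the SD is about 14.0 or less (n = 44) or about 12.8 or less (n = 37).
- True offset: pooled abdominal power is 89% (n = 66) or 82% (n = 56) at 1 mmHg, and 77% or 69% at 2 mmHg. It falls to 80% at an offset of about 1.8 mmHg (n = 66) or 1.2 mmHg (n = 56).

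**The case against.** The arithmetic is hard to dispute, so the best defence concerns consequence.

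- **Superseded plan.** The 38 and 44 appear under a pre-interim heading and supported a two-specialty plan that has been replaced. The primary analysis now uses all abdominal subjects and has 87–93% power. This stands, and it limits the severity. It does not remove the point, because 7.1, 11.2 and the synopsis still rely on the figure.
- **Meaning of the claim.** The primary endpoint is defined as a composite, for which no power target is given, and the post-interim text attaches no number to adequate power. Reading it as 80% is an inference. It is a fair one, since phase 2 is tied to the earlier calculation and that calculation targets 80% on three separate hypotheses. The point covers the pressure component only.
- **The 60% figure.** It assumes that all of the 15% loss by study end also removes 7-day pressure data. The documents give no rate of missing pressure data. At SD 14.8 and a true difference of 0, the firmer statement is therefore at most 73%.
- **The SD.** It comes from an earlier product, and the text does not say whether it describes per-subject means or individual readings. A smaller SD would help, as Step 4 shows.
- **Misreading.** The reported 95% interval lets a careful reader separate imprecision from a shift in pressure. That lessens the risk but does not make the power statement correct.

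**Conclusion.** The concern holds. The stated 80% power for 38 subjects is 62% under the planned test, and 80% requires 49 evaluable subjects, 11 more. For the pressure component, the claim of adequate power is supported for all 66 abdominal subjects at a true difference of 0. It is not supported for the 44 phase 2 subjects, who give 73% at best and 60% if 15% of pressure data are lost. Even if the device's mean equals the reference, that analysis would fail to show equivalence 27–40% of the time.

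This rests on the plan's own margin, SD, alpha and zero difference. It says nothing about wear time or exudate. It should be fixed, but the effect is limited: the affected analysis is secondary and the primary pooled analysis stays above 80% at the assumed difference.

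**What to change.** 1. **Section 11.1.** Replace the power sentence with: *For the planned TOST, 38 evaluable subjects give 62% power; 80% power needs 49 evaluable subjects.* Keep 44 and 88 as the record of the original recruitment plan, if preferred with a dated correction note, but remove the statement that 44 provides the power needed.
2. **Section 11.2 and synopsis.** Restrict the claim: *For the negative-pressure component (TOST, one-sided alpha 0.025 per test, margin 7 mmHg, SD 14.8, true difference 0), the primary analysis of all 66 abdominal subjects has 93% power, or 87% after 15% loss. The analysis of the 44 phase 2 subjects has 73% power, or 60% after 15% loss, and is supportive.* State the basis for wear time and exudate separately.
3. **Section 7.1.** Refer to the corrected text.
4. **Sections 10.2 and 10.4.** These define the s- populations by v8.0, while Section 22.1.3 allows entry under v9.0 once amendment 9 is approved. Align the definition with the phase 2 label. Otherwise n may be below 44 and the 73% would not apply.

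The cost is wording only. The test, margin and recruitment do not change. The drawback is a less favourable stated power for the phase 2-only analysis.
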